3.5.3. Vital Signs, including Height and Weight

Vital sign measurements are temperature, respiratory rate, pulse rate and blood pressures.

Height is collected at screening and weight is collected at pre- and post-treatment.

3.5.4. Physical Examinations

Complete physical examinations consist of assessments of general appearance; skin; head, eyes, ears, nose and throat; mouth, heart; lungs; breast (optional); abdomen; external genitalia (optional); extremities; neurologic function; and lymph nodes. A targeted physical examination will include, at a minimum, assessments of the skin, heart, lungs, and abdomen and examination of body systems where there are symptom complaints by the participant.

4. ANALYSIS SETS

Data for all subjects will be assessed to determine if subjects meet the criteria for inclusion in each analysis population described below prior to unblinding and releasing the database and classifications will be documented per standard operating procedures.

4.1. Full Analysis Set

The Full Analysis Set (FAS) is defined as all subjects who have been randomized and who have received at least one dose study of treatment. Subject is assigned to the randomized treatment group regardless of actual treatment received. Analyses for endpoints that are defined based on a threshold of change from baseline (eg, NRS4) will also require the baseline value to be equal to or greater than that threshold (eg, for NRS4, the baseline value needs to be ≥ 4).

4.2. Per Protocol Analysis Set

The Per Protocol Analysis Set (PPAS) is defined as a subset of FAS who had no major protocol violations. The subjects excluded from the PPAS will be determined and documented before the study is unblinded. Supportive analyses for the primary endpoint will be performed using the PPAS. This set will include subjects who:

- Were eligible for the study by way of meeting key inclusion criteria and none of the key exclusion criteria.
- Had valid and non-missing biopsies at baseline and per protocol schedule.

- Did not take a protocol-prohibited medication for the primary diagnosis prior to completion of the study dosing period (Visit 10/Week 12).
- Took the correct randomized treatment for at least 80% and at most 120% of the assigned amount until completion of the study dosing period (Visit 10/Week 12).
- Had no other major protocol violations as determined by the clinical team prior to database lock. A major protocol violation in this context is one that is likely to affect materially the efficacy responses of the patient and will be defined by the clinical team before database is locked and any analysis is performed for this study.

These items will either be assessed by programmed checks of the data or be determined by clinical review prior to unblinding of study treatment.

4.3. Safety Analysis Set

The Safety Analysis Set (SAF) will be defined as all subjects who receive at least one dose of study medication classified according to actual study treatment received. The safety analysis set is the primary population for treatment administration / compliance and safety. A randomized but not treated subject will be excluded from the safety analyses.

5. GENERAL METHODOLOGY AND CONVENTIONS

The final analysis and reporting of results will be performed after the completion of the study and the database is locked.

5.1. Hypotheses and Decision Rules

There will be no formal hypothesis testing, but the point estimates and 95% two-sided confidence intervals will be reported for the biomarker endpoints, secondary efficacy CCI [REDACTED] endpoints. No adjustments for multiplicity will be performed. Safety endpoints will be summarized descriptively through appropriate data tabulations, descriptive statistics, categorical summaries, and graphical presentations.

5.1.1. Estimands

The primary objective of this study is to assess the effects of PF-04965842 on lesional and non-lesional skin biomarkers of adult participants with moderate-to-severe AD. A hypothetical estimand will be used for estimation. The following estimand attributes will be considered:

- Population: Participants with moderate-to-severe AD as defined by the inclusion criteria and with a valid baseline and Week 12 assessment;

- Variable: Fold-change from baseline in the biomarkers for general inflammation (MMP12), hyperplasia (K16), Th2 immune response (CCL17, CCL18, CCL26), and Th22 immune response (S100A8, S100A9, S100A12);
- Intercurrent event: All data collected will be utilized;
- Population-level summary: Mean fold-change from baseline within each treatment group.

Some secondary objectives require analyses of binary endpoints for which, a composite estimand with the following attributes will be considered:

- Population: Participants with moderate-to-severe AD as defined by the inclusion criteria and with a valid baseline;
- Variable: Binary outcome measures such as responder-based endpoints. Participants who discontinue from the study treatment for any reason are defined as non-responders after that point;
- Intercurrent event: The intercurrent event is captured through the variable definition;
- Population-level summary: Proportion of participants who are responders in each treatment group and differences in proportions of responders between each active dose and placebo.

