7. DISCONTINUATION OF STUDY INTERVENTION AND PARTICIPANT DISCONTINUATION/WITHDRAWAL

7.1. Discontinuation of Study Intervention

In certain instances, it may be necessary for a participant to permanently discontinue study intervention (ie, study treatment). If study intervention is permanently discontinued, the participant will remain in the study to be evaluated for EOT assessments (per [Schedule of Activities](#)).

Note that discontinuation of study treatment does not represent withdrawal from the study. Refer to [Appendix 10](#) for discontinuation criteria.

See the [Schedule of Activities](#) for data to be collected at the time of intervention discontinuation and follow-up and for any further evaluations that need to be completed.

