9.4.1. Analysis of the Primary Endpoint

The population for the primary analysis will be all participants in the FAS having valid biomarker data at baseline and Week 12.

The primary endpoints in this study include mean fold-changes for the following biomarkers:

- General inflammation (MMP12);
- Hyperplasia (K16);

- Th2 (CCL17, CCL18, CCL26);
- Th22 (S100A8, S100A9, S100A12).

In each participant, expression levels from RT-PCR will be normalized to the housekeeping gene RPLP0 (validated in other studies) by negatively transforming the Ct values to $-dCt$, obtaining an equivalent to log2 scale expression values (reporting unit: log2 [Expression/RPLP0]). The expression values below detection will be estimated for each gene as the 20% of the minimum of unlogged values across all samples (which is equivalent to subtracting 2.321928 from the $-dCt$ minimum value). The expression levels below detection may provide important information about some markers that significantly change with treatment (eg, the expression may decrease below the level of detection after treatment), therefore this imputation is an important step in the analysis.

RT-PCR expression data in log2 scale will be modeled using a mixed effect model with Treatment, Time Point, and Tissue Type as a fixed effect and a random intercept for each participant. This model will yield unbiased estimates and valid inferences in the presence of a missing data mechanism that is missing at random (MAR). ²⁹ This approach introduces less bias than restricting the analysis for participants with complete observations and is consistent with estimation of a hypothetical estimand. Contrasts will be used to estimate the log2 fold-changes for each treatment group. Fold-changes will be computed by obtaining the antilog of log2 fold-changes. Point estimates and 95% confidence intervals (CIs) will be obtained for the fold-change from baseline in the biomarker values for each treatment group based on this model.

Correlation analyses will be performed to assess if the fold-change from baseline in biomarkers correlates with change (from baseline) in the clinical efficacy endpoints such as IGA, EASI, and Peak Pruritus NRS.

Supportive analyses for the primary endpoint will also be performed using the PPAS.

[figure not shown]

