5.2.1. Analysis of Primary Endpoint

The population for the primary analysis will be all participants in the FAS having valid biomarker data at baseline and Week 12.

The primary endpoints in this study include mean fold-changes for the following biomarkers:

- General inflammation (MMP12);
- Hyperplasia (K16);
- Th2 (CCL17, CCL18, CCL26);
- Th22 (S100A8, S100A9, S100A12).

In each participant, expression levels from RT-PCR will be normalized to the housekeeping gene RPLP0 (validated in other studies) by negatively transforming the Ct values to $-dCt$, obtaining an equivalent to log2 scale expression values (reporting unit: log2 [Expression/RPLP0]). The expression values below detection will be estimated for each gene as the 20% of the minimum of unlogged values across all samples (which is equivalent to subtracting 2.321928 from the $-dCt$ minimum value). The expression levels below detection may provide important information about some markers that significantly change with treatment (eg, the expression may decrease below the level of detection after treatment), therefore this imputation is an important step in the analysis.

RT-PCR expression data in log2 scale will be modeled using a mixed effect model with Treatment, Time Point, and Tissue Type as a fixed effect and a random intercept for each participant. This model will yield unbiased estimates and valid inferences in the presence of a missing data mechanism that is missing at random (MAR).¹ This approach introduces less bias than restricting the analysis for participants with complete observations. Contrasts will be used to estimate the log2 fold-changes for each treatment group. Fold-changes will be computed by obtaining the antilog of log2 fold-changes. Point estimates and 95% confidence intervals (CIs) will be obtained for the fold-change from baseline in the biomarker values for each treatment group based on this model.

Correlation analyses will be performed to assess if the fold-change from baseline in biomarkers correlates with change (from baseline) in the clinical efficacy endpoints such as IGA, EASI, and Peak Pruritus NRS.

Supportive analyses for the primary endpoint will also be performed using the PPAS.

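### The primary analysis admits only participants with Week 12 data, against its own missing-at-random rationale, and carries a hypothetical-estimand label that its all-data rule does not support

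*SAP*

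**What the plan says.** **Label and data rule.** SAP 5.1.1 introduces the primary estimand with "A hypothetical estimand will be used for estimation". The attribute list beneath it reads "Intercurrent event: All data collected will be utilized". No intercurrent event is named and no hypothetical scenario is described. Protocol 9.1.1 has the same all-data attribute without the label. Protocol 9.4.1 says that the mixed-model approach "is consistent with estimation of a hypothetical estimand".

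**Population.** SAP 5.1.1 defines the population as participants with moderate-to-severe AD "as defined by the inclusion criteria and with a valid baseline and Week 12 assessment". SAP 5.2.1 repeats the condition: "The population for the primary analysis will be all participants in the FAS having valid biomarker data at baseline and Week 12". Protocol 9.1.1 and 9.4.1 impose the same requirement. SAP 6.1.1 gives the population simply as FAS, but refers to 5.2.1 for the method.

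**Rationale.** SAP 5.2.1 models log2 expression with a random intercept per participant, claims validity under MAR, and adds: "This approach introduces less bias than restricting the analysis for participants with complete observations". Protocol 9.4.1 makes the same argument. The primary summary in SAP 6.1.1 is the Week 12 fold-change, with no explicit imputation.

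**Schedule.** Lesional biopsies are required at baseline, Week 4 and Week 12 and are optional at Week 2. Protocol 7.1 adds: "Note that discontinuation of study treatment does not represent withdrawal from the study".

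**The concern.** Two things conflict in the current text, without any reliance on the SAP's version history.

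First, a hypothetical strategy targets the outcome had some event not happened. It must name the event and say what is done with data collected after it. A rule that uses all data regardless of events is treatment policy. The report would put one name on an estimate produced by the other.

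Second, the reason for preferring a likelihood-based mixed model is that people who leave before Week 12 still inform the Week 12 estimate through their earlier samples. Requiring Week 12 data for entry gives that up. It also selects each arm on something that happens after randomisation. This matters because both documents plan to read the active-arm fold-changes against placebo and to attribute a change seen only on drug to its mechanism of action. With no hypothesis tests planned (SAP 5.1), these estimates and their intervals are the primary result.

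**Working it through.** **1. The plan's own precision figure.** Inputs from SAP 2.2 and protocol 9.2: n = 17 per group, SD 5, half-width 3.2, 95% CI. The formula is P(χ² on n−1 df ≤ (n−1)·[3.2√n/(5t)]²), with t = 2.120 on 16 df. Then 3.2 × 4.123 = 13.194; 13.194/(5 × 2.120) = 1.245; 16 × 1.245² ≈ 24.8; and P(χ² on 16 df ≤ 24.8) = 0.926. This agrees with the stated 92%. The sample-size statement is not in question, but it takes all 17 as evaluable.

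**2. Does the label change which biopsies enter?** The all-data rule appears in protocol 1.1, 3 and 9.1.1 and in SAP 5.1.1. Neither SAP 5.2.1 nor SAP 6.1.1 excludes a biopsy because of an intercurrent event. All-data is therefore the only operational instruction, and deleting the label alone leaves the dataset unchanged.

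**3. Does the Week 12 requirement change who enters?** Consider FAS participants with a baseline lesional biopsy:

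- Baseline, Week 4 and Week 12: included.
- Baseline and Week 12, with Week 4 missing: included. MAR covers the gap, but the gap is not at a time point in the primary contrast.
- Baseline and Week 4 (or optional Week 2), with no Week 12: excluded. This is the pattern for which the MAR argument matters to the Week 12 contrast.

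After the restriction, everyone left has data at both ends of the lesional contrast. The MAR argument has almost nothing left to do for it.

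**4. Direction and form of the bias.** In one arm, let n participants have a baseline and an early post-baseline biopsy, of whom n_d lack Week 12. Let x_C and x_D be the mean early log2 changes in those with and without Week 12 data, and b the slope of Week 12 change on early change. This one-early-visit regression simplifies what the mixed model does.

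- Restricted estimate: y_C.
- Estimate using everyone under MAR: y_C + b(n_d/n)(x_D − x_C).
- Difference, restricted minus all: b(n_d/n)(x_C − x_D) on the log2 scale. The ratio of fold-changes is 2 to that power.

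If completers had the larger early reductions, x_C − x_D is negative. With b positive, the restricted analysis then overstates the reduction. If the two groups had equal early change, the difference is zero.

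The documents give none of n_d, b or x_C − x_D. Taking n = 17 and assuming n_d from 1 to 4, n_d/n runs from 1/17 = 0.06 to 4/17 = 0.24. The shift is then 0.06 to 0.24 of b(x_C − x_D), and no further figure can be supported.

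**The case against.** **The label is stray wording.** This stands. SAP 5.2.1 omits the clause that protocol 9.4.1 carries, and in the protocol the clause is attached to the treatment of missing values, not to discarding observed ones. It still needs removing: SAP 5.1.1 applies the label to the whole estimand, and with Week 12 data required there are few unobserved Week 12 values for it to describe.

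**A reader might infer that the set of biopsies is undecided, or that the two strategies would give materially different fold-changes.** The documents do not support either. The data rule is explicit. A material difference would need several participants biopsied at Week 12 while off drug. Those who meet discontinuation criteria go to the end-of-treatment visit and then to a follow-up with no scheduled biopsy (protocol Appendix 10 and Schedule of Activities). The remaining routes, such as a voluntary stopper who stays in the study, may be rare. Prohibited AD medication could move the estimate in the opposite direction.

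**A reader might infer that the restriction costs precision, since the 92% assurance falls to 82% (0.823) with 15 evaluable.** The arithmetic is right, but it measures the absence of Week 12 biopsies. Lifting the restriction would not supply them.

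**The Week 12 requirement is deliberate and consistent, and is not a full complete-case rule.** True. It appears in all four sections, and Week 4, optional Week 2 and optional Week 12 non-lesional samples may still be missing, so MAR keeps some role. That does not reconcile it with the stated rationale for the contrast reported as primary.

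**An on-treatment analysis is already planned.** Also true. But the PPAS (SAP 4.2) itself requires biopsies per schedule, so it does not bring back those without Week 12.

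**Conclusion.** The point holds in two parts of unequal weight.

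The hypothetical label in SAP 5.1.1 and protocol 9.4.1 is wrong for a rule that uses all collected data. The consequence is a mislabelled estimate, not a different one.

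The Week 12 requirement is the part that can change results. It contradicts the plan's reason for choosing the mixed model, discards collected Week 2 and Week 4 biopsies, and conditions on a post-randomisation outcome. Its size cannot be established from the documents. It depends on how many participants per arm have an early biopsy but no Week 12 biopsy, and on whether their early response differed. It also depends on how early-termination biopsies are classed: the Schedule of Activities labels the Week 12 visit EOT/ET, while SAP Appendix 2 starts the Week 12 window at Day 72. If that window applies to biopsies, early leavers are excluded; if every early-termination biopsy counts as Week 12, fewer are.

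The advantage of the wider population rests on MAR being more plausible than missingness unrelated to response. The plan already makes the MAR assumption.

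**What to change.** 1. Remove the Week 12 requirement from protocol 9.1.1 and 9.4.1 and SAP 5.1.1 and 5.2.1. Let FAS participants with a baseline and at least one post-baseline biopsy enter the primary mixed model, with the Week 12 fold-change still the reported contrast. Point SAP 6.1.1 to the same definition.
2. Report the analysis of participants with baseline and Week 12 data as a sensitivity analysis.
3. Delete the hypothetical label in SAP 5.1.1 and protocol 9.4.1. Name treatment policy, stating that all collected biopsies are used regardless of treatment discontinuation or prohibited medication. Keep the PPAS as the supportive on-treatment analysis.

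**Cost.** No new data are needed, but this is more than editing: the primary population is redefined. SAP section 2 says that major changes to the primary analysis also go into a protocol amendment. Some participants would contribute to Week 12 only through the model under MAR, which borrows from people who stayed and should be stated beside the treatment-policy name. Week 12 precision would be only partly recovered, and anyone with no post-baseline biopsy would still be left out.

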6.5.2. Prohibited Medications and Treatments

Participants are required to discontinue and avoid using certain medications and treatments (see [Inclusion Criteria](#) and [Exclusion Criteria](#) and [Appendix 7](#)). Participants should be instructed at each visit to contact the study site investigator promptly if there are any intended changes or additions to concomitant medications.

All medications and treatments that could affect AD must be discontinued except oral antihistamines.

Due to the potential to affect AD with ultraviolet light exposure, participants must also avoid prolonged exposure to the sun and not to use tanning booths, sun lamps or other ultraviolet light sources during the study.

Participants who received prior treatment with systemic JAK inhibitors are to be excluded from the study.

Herbal medications with unknown properties or known beneficial effects for AD must be discontinued at least 4 weeks before the first dose of study intervention.

The Pfizer study team is to be notified of any prohibited medications taken during the study. After consulting with the Pfizer clinician, the investigator will make a judgment on the ongoing eligibility of any participant with prohibited medication use during the study.

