5.2.3. Analyses of Other Endpoints

The responses based on IGA, EASI (eg, EASI-75), and severity scale of the Peak Pruritus NRS will be summarized descriptively by visit and treatment. The difference of the improvement from baseline between each PF-04965842 dose and placebo will also be derived.

If a participant withdraws from the study, then this participant will be considered a non-responder after withdrawal for any binary valued clinical efficacy endpoint.

CCI

CCI

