5.3. Methods to Manage Missing Data

In general, for analyses using descriptive statistics, missing values will not be explicitly imputed. In addition, for safety endpoints, missing values will not be imputed.

For the responses based on IGA, EASI (eg, EASI-75), and severity scale of the Peak Pruritus NRS, if a participant withdraws from the study, then this participant will be considered a non-responder after withdrawal for any binary valued clinical efficacy endpoint.

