6.3.3. EASI50, EASI75 and EASI90 Response

- Summary: Proportion of subjects with EASI response at Weeks 2, 4, 8 and 12;
- Population: FAS;
- Statistical Method: Descriptive (n, %). Visit windows will be used as described in Appendix 2;
- Missing Data: Missing data arising due to subject dropout are considered “non-response”.

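### No visible IGA, EASI or NRS4 responder rule treats prohibited AD medication as non-response, so a response reached with other AD therapy can count for the assigned monotherapy arm

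*SAP*

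**What the plan says.** **Non-response triggers.** Three kinds are visible.

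- *Stopping study treatment.* SAP 5.1.1: "Participants who discontinue from the study treatment for any reason are defined as non-responders after that point". The next attribute reads "Intercurrent event: The intercurrent event is captured through the variable definition", so nothing outside that definition is covered.
- *Leaving the study.* SAP 5.2.3: "If a participant withdraws from the study, then this participant will be considered a non-responder after withdrawal". SAP 5.3 and Protocol 9.4.2.1 carry the same rule.
- *Missing data from dropout.* SAP 6.3.1 to 6.3.3, for NRS4, IGA and EASI-50/75/90: "Missing data arising due to subject dropout are considered" non-response.

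**Prohibited AD treatment.** Protocol 6.5.2: "All medications and treatments that could affect AD must be discontinued except oral antihistamines". Protocol 6.5.1 also permits non-medicated emollient. If a prohibited medication is taken, the sponsor's team is told and, after consulting the sponsor's clinician, "the investigator will make a judgment on the ongoing eligibility of any participant with prohibited medication use during the study". Such use is not among the mandatory discontinuation criteria in Protocol Appendix 10 or the reasons for leaving the study in Protocol 7.2.

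**Analysis sets.** SAP 4.1 keeps every dosed participant in the randomized arm of the FAS. SAP 4.2 removes from the PPAS anyone who took a prohibited medication for AD before Week 12, and describes the PPAS as supportive for the primary (biomarker) endpoint. SAP 6.3.1 to 6.3.3 give only FAS-based populations. SAP Appendix 1 nevertheless lists PPAS rows for Week 12 IGA, Week 12 EASI-75 and NRS4.

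**The concern.** This is a monotherapy trial, and the SAP has already chosen a composite strategy for its responder endpoints: certain events turn an observed response into a failure. Treatment of AD with something other than the assigned tablets is an obvious candidate event. The SAP itself regards it as serious enough to disqualify a participant from the PPAS. Yet a participant who uses such treatment, is allowed to stay on tablets and then reaches IGA 0/1, EASI-75 or NRS4 is scored by the observed value, as a success of the assigned arm.

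At stake are the response proportions and the dose-minus-placebo differences that SAP 5.1.1 names as the population-level summary. With small arms, a few such participants can change these visibly. If use were commoner where the assigned treatment is failing, the placebo rate would rise and the differences would shrink. That pattern is plausible, but the documents do not establish it.

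**Working it through.** **1. The plan's own design figure.** SAP 2.2 gives about a 92% chance that the 95% CI half-width for a mean fold-change is at most 3.2, with n = 17 and SD = 5. The check is P(χ²₁₆ ≤ 16 × (3.2 × √17 / (2.1199 × 5))²) = P(χ²₁₆ ≤ 24.8) = 0.926, which agrees. This concerns biomarkers only. The point here does not depend on it, beyond the arm size of 17.

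**2. Following one participant through the rules.** Take a participant who uses a prohibited AD treatment, is judged able to continue, takes the tablets to Week 12 and attends every visit.

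- SAP 5.1.1: treatment not stopped, so not triggered.
- SAP 5.2.3 and 5.3: study not left, so not triggered.
- SAP 6.3.1 to 6.3.3: nothing missing, so not triggered.
- SAP 4.1: stays in the FAS under the randomized arm.

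The observed score decides. A participant taken off study treatment because of the medication would be a non-responder under SAP 5.1.1, so the gap is confined to those who continue.

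**3. What the PPAS rows cover.** They remove the user instead of counting a failure. They also remove participants for unrelated reasons, such as missing biopsies or compliance outside 80% to 120%, so the FAS-to-PPAS contrast does not isolate this event. There is no PPAS row for EASI-50 or EASI-90, and the listed rows do not match the PPAS role in SAP 4.2 or the populations in SAP 6.3.

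**4. Size per case.** 1/17 = 0.0588, or 5.9 percentage points in the affected arm. With k such responses in an active arm and m in placebo, the difference shifts by (k − m)/17. It can go either way.

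**5. Hypothetical illustration.** Protocol 2.2.2 gives Week 12 IGA response in the Phase 2b study as 44.5% (200 mg), 27.8% (100 mg) and 6.3% (placebo). These agree with its stated differences: 44.5 − 6.3 = 38.2 and 27.8 − 6.3 = 21.5. Assume m cases in placebo and none in the active arms, so the placebo rate is 6.3% + m/17:

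| m | Placebo | 200 mg difference | 100 mg difference |
|---|---|---|---|
| 0 | 6.3% | 38.2 | 21.5 |
| 1 | 12.2% | 32.3 | 15.6 |
| 2 | 18.1% | 26.4 | 9.7 |
| 3 | 23.9% | 20.6 | 3.9 |

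Alternatively, assume that a share u of placebo non-responders use other AD treatment and a share q of those respond. The placebo rate is then 0.063 + 0.937 × u × q. For u from 5% to 30% and q from 25% to 50% it runs from 7.5% to 20.4%. The 200 mg difference runs from 37.0 down to 24.1 points and the 100 mg difference from 20.3 down to 7.4. The values of m, u and q are all assumptions.

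**The case against.** **Already examined through the PPAS.** A reader might infer that the plan ignores prohibited medication in its efficacy analyses. It does not: comparing FAS and PPAS rates for Week 12 IGA, Week 12 EASI-75 and NRS4 would give some indication. This narrows the gap but, for the reasons in step 3, does not close it.

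**Few participants are exposed.** There is no planned rescue pathway, the sponsor's clinician is consulted, and the case arises only if the participant both continues and responds. This stands. The documents give no frequency, and it may be zero.

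**An estimand choice.** Counting the observed response whatever else was taken is a recognised treatment-policy strategy. That is fair, but SAP 5.1.1 does not adopt it for this event; it adopts a composite strategy and leaves the event unnamed.

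**A fixed placebo inflation.** It is tempting to start from the Phase 2b placebo EASI-75 rate of 15.6% (2.65 of 17) and conclude that one to three cases would give 21.5% to 33.2%. The documents do not support this as an estimate. The count and the arm are assumed. Protocol 2.2.2 gives the same three figures both as percent change in EASI and as EASI-75 rates, and its stated 200 mg difference of 41.8 is not 63.7 − 15.6 = 48.1. How that study handled prohibited medication is also not stated, so its placebo rates, including the IGA rate used above, may already contain such responses.

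**Limited consequence.** There is no hypothesis test, the responder endpoints are descriptive, and neither the sample size nor any decision rule uses them. This stands.

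**Conclusion.** The point holds for IGA and EASI on visible, unredacted rules. For NRS4 it holds only as the absence of a visible rule: SAP Appendix 3, which SAP 3.2 cites for the NRS derivation, is redacted, as is some text after SAP 5.2.3. A reader might infer that no NRS4 rule exists, but that cannot be shown.

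The firm size is 5.9 points per affected participant, assuming all 17 in an arm are dosed and counted. Any total shift, and its direction, rests on assumed frequency and arm. Type I error and the design precision are untouched.

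A reader might also infer that recoding responders would protect the mechanistic correlations. It would not. SAP 5.2.1 correlates biomarker fold-change with change from baseline in IGA, EASI and NRS, and those values stay the same whatever the responder rule. They need separate handling.

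This is an inexpensive improvement to make before unblinding. It does not invalidate the plan.

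**What to change.** 1. In SAP 5.1.1, and to match in 5.2.3, 5.3 and 6.3.1 to 6.3.3, add a composite event such as: *a participant who uses a protocol-prohibited AD treatment after the first dose, as identified in the blinded review for the PPAS, is a non-responder from that point on.* Oral antihistamines and non-medicated emollient stay outside it.
2. Keep the as-observed FAS responder result as a sensitivity analysis.
3. Flag later values of continuous EASI, IGA, NRS and %BSA. Show those summaries and the biomarker correlations with and without the flagged visits.
4. Reconcile the PPAS rows in Appendix 1 with SAP 4.2 and 6.3.

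**Cost.** SAP wording, one flag and a few repeat summaries. Protocol 6.5 already requires concomitant medications to be recorded with an AD indication where it applies and with start and stop dates. SAP 4.2 already settles PPAS exclusions before unblinding.

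**Downside.** Responder rates may fall in any arm, by 5.9 points per affected responder. A brief early use would count as failure at every later visit; the as-observed sensitivity analysis shows how much that matters. No clinical management rule changes.
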